Study Phase II is an 8-week, “double-blind” treatment period that commences at Visit 2 (randomization visit). Subsequent evaluation will be scheduled at one-week intervals for the first 2 visits, then two-week intervals for the next 3 visits, concluding at Visit 7, or upon termination. During this treatment phase, patients will take one tablet of study medication (fluoxetine 20 mg, or placebo) daily and will use the treatment device (light box or ion generator) for 30 minutes daily.

At Visit 2, patients will be discontinued from the study if they show significant spontaneous response. Spontaneous response is defined as greater than 25% reduction of Ham-17 between Visit 1 and Visit 2, or if the Ham-17 at Visit 2 is 19 or less.

At Visit 2, subjects will be instructed on the use of the assigned treatment device and medication, and will then complete an Expectation of Response questionnaire modeled on a questionnaire by Borkovec and Nau (1972). Subjects will take home the treatment device to use for the duration of the study. Adherence to the protocol will be reinforced and monitored at each study visit. A daily log will be completed by subjects to record their use of the treatment device, and they will telephone the Centre and leave a time-stamped voice-mail message each day when using the device. These logs will be inspected at each visit throughout the study and recorded on the web-CRF.

In summary, the following clinical efficacy parameters will be recorded at Visit 2.

1. Expectation of Response Questionnaire (Visit 2 only)
2. Ham-17

The following clinical efficacy and safety parameters will be repeated at Visits 2 through 7.

1. Combined MADRS/Ham-24 (by telephone with a rater blind to treatment condition using the SIGMA/SIGH-SAD)
2. CGI (Severity and Improvement)

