A secondary confirmatory analysis will also be conducted using a mixed-effects model with repeated measures (MMRM), under the missing at random framework (Gueorguieva and Krystal, 2004). The baseline MADRS score will be used as a covariate under this model. This model will include treatment condition and visit factors as class fixed effects and subject as random effect as well as two interaction terms between treatment condition by visit and covariate by visit, and subject as random. The treatment condition factor will have 4 levels (two monotherapies, one placebo condition, and one combination condition) and the visit factor will have 4 levels (each of the 4 treatment visits). This model using all available post-baseline evaluation in Phase II will provide the baseline adjusted least-squares means (LS-means) estimates at Week 8 by treatment condition, as well as the differences of these estimates versus placebo conditions, with their corresponding standard errors, degrees of freedom, t-test statistics and associated 95% confidence intervals. The t-test statistic at Week 8 will be used to determine the statistical significance of the primary efficacy comparisons of active versus placebo conditions.

L. Informed Consent and Ethical Considerations

The investigator will prepare a written Informed Consent Document (ICD). The subject will read the ICD and the investigator will answer any questions he/she may have. The subject must indicate willingness to participate in the study by signing the ICD. The document must also be signed by a witness and an investigator. A copy of the signed ICD will be submitted to the Study Coordinator.

This study will be conducted according to guidelines established by Good Clinical Practice (Food and Drug Administration, www.fda.gov/oc/gcp/regulations.html). The Institutional Review Boards (IRBs, or research ethics committees) of each participating site must approve the protocol and ICD. Each investigator will provide the Study Coordinator with evidence that their IRB has approved the study before subjects are entered at that site.

M. Publications and Communications

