This trial will be registered at www.clinicaltrials.com and at the Cochrane Collaboration clinical trials registry in accordance with the policy from the International Committee of Medical Journal Editors (De Angelis et al, 2004). The results of this trial will be presented at scientific conferences and published, using the CONSORT guidelines, in a peer-reviewed scientific journal.

N. List of Trial Site Investigators

[name]/[name]
Vancouver, BC.

[name]
Winnipeg, MB.

[name]/[name]
Toronto, ON.

[name], MDCM
Montreal, QC

[name]
St. John, NB.

[name]
Calgary, AB

[name]
Calgary, AB

O. References

Please refer to Research Proposal, p.12 of the Research Module.

P. Appendix

Summary of Procedures

Item	Visit 1 Screen	Visit 2 Week 0	Visit 3 Week 1	Visit 4 Week 2	Visit 5 Week 4	Visit 6 Week 6	Visit 7 ^a Week 8
Physician: ICD signed	X						
Physician: MINI/C-CASA	X						
Physician: Eligibility	X						
Physician: Demographic info	X						
Physician: Ham-17	X	X					
Study Coordinator (SC): SPAQ*/ASRS*/RSQ*	X						
SC/Web: Expectation of Response*		X					
Telephone: MADRS+Ham-24		X	X	X	X	X	X
Physician: CGI (-S and -I)		X	X	X	X	X	X
SC: Health Economic Assessment		X	X	X	X	X	X
SC/Web: QIDS-SR*		X	X	X	X	X	X
SC/Web: Adverse Events Scale*		X	X	X	X	X	X
SC/Web: FSS*		X		X	X	X	X
SC/Web: LEAPS*		X			X		X
SC/Web: Q-LES-Q*		X			X		X
SC/Web: PSQI*		X			X		X
SC/Web: MEQ*		X			X		X
SC: Weight		X			X		X
SC: Height		X					
SC: Device/drug instructions		X	X	X	X	X	
SC: Handout/return device		X					X
Physician: Debrief							X

^a or Termination visit, if patient withdraws.

* patient-rated.

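### The MMRM visit factor has 4 levels but the MADRS is rated at 5 post-baseline visits, and the stated random subject effect, fitted as written, gives a Week 8 standard error that is right only if variance is constant

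*Protocol*

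**What the plan says.** Section K (Data Analysis) of the protocol describes an MMRM with baseline MADRS as covariate and treatment and visit as fixed factors. On the visit factor it says "the visit factor will have 4 levels (each of the 4 treatment visits"). The sentence that follows begins "This model using all available post-baseline evaluation in Phase II". On within-subject dependence it lists "subject as random effect as well as two interaction terms between treatment condition by visit and covariate by visit, and subject as random"; no residual covariance structure is named.

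Section F (Study Phase II) schedules the visits after randomization at "one-week intervals for the first 2 visits, then two-week intervals for the next 3 visits, concluding at Visit 7". Of the list that starts with the combined MADRS/Ham-24 telephone rating, it says "The following clinical efficacy and safety parameters will be repeated at Visits 2 through 7". In the Appendix (Summary of Procedures), the row "Telephone: MADRS+Ham-24" is marked at Week 0 and at Weeks 1, 2, 4, 6 and 8.

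On the role of the model, section K makes an ANOVA on LOCF change scores the main analysis and calls the MMRM a secondary, confirmatory one. It then closes by giving the MMRM's Week 8 t-test the job of deciding significance for the primary active-versus-placebo comparisons.

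**The concern.** There are two separate faults in one model statement.

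**Visit count.** Five ratings cannot be fitted with a four-level visit factor. Whoever programs the model must either change the number or leave out a visit that the protocol does not name.

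**Covariance.** A random subject effect with independent residuals of one variance assumes the same variance at every visit and the same correlation between any two visits. The test of interest is at Week 8 alone, but its standard error is then built from a variance pooled over all visits. If patients spread out as treatment proceeds, the small early variances pull the Week 8 standard error down.

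The design makes such spreading plausible, though it does not prove it. Entry requires a Ham-17 of at least 20, and patients at 19 or less at Visit 2 are discontinued, which narrows the range at the start. Baseline MADRS enters with a covariate-by-visit term and may well explain more of Week 1 than of Week 8.

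At stake is the error rate of a test that section K says decides the primary comparisons, for which section D (Sample Size) sets a Bonferroni-corrected two-sided level of 0.017.

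**Working it through.** **1. Visit count.** Two one-week steps and three two-week steps after Visit 2 give Weeks 1, 2, 4, 6 and 8, which are Visits 3 to 7: five visits. The Appendix row gives the same five. The stated 4 is not reproduced. Counting baseline gives 6. Counting two-weekly visits only (Weeks 2, 4, 6, 8, as for the FSS) gives 4, but the MADRS is not on that schedule.

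**2. Week 8 standard error under a random intercept.** With complete data and separate means for each treatment and visit, the Week 8 contrast is the difference of Week 8 means. Its true standard error is SD(Week 8) × √(2/n). The random-intercept model replaces SD(Week 8) by the root of the average visit variance, so

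ratio = √(mean of visit variances) / SD(Week 8), and
actual two-sided alpha = 2 × [1 − Φ(z × ratio)], with z = 1.960 at nominal 0.05 and 2.387 at nominal 0.017.

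Inputs: n = 54 per arm (section D). The protocol gives no MADRS SD and no between-visit correlation; its only SD is 8, for secondary scales such as quality of life. All visit SDs below are therefore assumptions, to be read as SDs after baseline adjustment.

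Worked case, SDs 5, 6, 7.5, 8.5, 9:
- Mean variance = (25 + 36 + 56.25 + 72.25 + 81)/5 = 54.1, with root 7.355; ratio = 7.355/9 = 0.817.
- Standard errors: model √(2 × 54.1/54) = 1.42; true √(2 × 81/54) = 1.73.
- Alpha: 1.960 × 0.817 = 1.60 gives 0.109; 2.387 × 0.817 = 1.95 gives 0.051.

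| Assumed SDs, Weeks 1, 2, 4, 6, 8 | Ratio | Alpha at nominal 0.05 | Alpha at nominal 0.017 |
|---|---|---|---|
| 9, 8.5, 8, 7.5, 7 | 1.147 | 0.025 | 0.006 |
| 8 throughout | 1.000 | 0.050 | 0.017 |
| 7, 7.25, 7.5, 7.75, 8 | 0.939 | 0.066 | 0.025 |
| 6, 6.5, 7, 7.5, 8 | 0.879 | 0.085 | 0.036 |
| 5, 6, 7.5, 8.5, 9 | 0.817 | 0.109 | 0.051 |
| 4, 5.5, 7, 8, 9 | 0.770 | 0.131 | 0.066 |

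**3. Simulation with dropout.** Setup: four arms of 54, 20% monotone dropout completely at random after Week 1, correlation 0.8 per two weeks (assumed), no baseline covariate, nominal 5%.

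| SDs (runs) | Model | Mean SE / empirical SD | Rejection |
|---|---|---|---|
| 5 to 9 (600) | random intercept, 5 visits | 1.462 / 1.826 = 0.80 | 12.7% |
| 5 to 9 (600) | random intercept, Week 1 omitted | 1.591 / 1.834 = 0.87 | 9.7% |
| 5 to 9 (600) | unstructured, 5 visits | 1.864 / 1.815 = 1.03 | 4.0% |
| 5 to 9 (600) | unstructured, Week 1 omitted | 1.875 / 1.827 = 1.03 | 4.0% |
| 9 to 7 (300) | random intercept, 5 visits | 1.650 / 1.440 = 1.15 | 3.3% |
| 9 to 7 (300) | unstructured, 5 visits | 1.442 / 1.406 = 1.03 | 5.7% |
| 8 throughout (250) | random intercept, 5 visits | 1.623 / 1.719 = 0.94 | 7.6% |
| 8 throughout (250) | unstructured, 5 visits | 1.663 / 1.689 = 0.98 | 6.4% |

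The Monte Carlo standard error at a true 5% is √(0.05 × 0.95/600) = 0.9 points for 600 runs and 1.4 points for 250. The constant-SD result is thus within noise of nominal and suggests a small effect at most. The unstructured model stays near nominal in all three cases.

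**The case against.** **The random effect need not mean compound symmetry.** Section K is silent on the residual covariance. A random subject effect does not rule out a richer residual structure, the label MMRM often implies an unstructured one, and a statistical analysis plan that is not to hand may say so. Degrees of freedom and fallback rules commonly belong there too. This stands, and it makes the covariance point conditional. It does not remove it: the protocol names the random effect twice and nothing else, and beside an unstructured covariance that effect would be redundant.

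**The direction of the error is not known.** No visit variances are given, and with falling variance the test is conservative. This also stands. A reader might infer that the standard error is too small as a matter of fact; the documents support only that it is so if variance rises.

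**A visit is not shown to be lost.** A reader might infer from the four levels that one visit's data are discarded. The next sentence of section K says that all post-baseline evaluations are used, and no visit is named for omission, so a miscount is the likelier reading. Nor can one conclude that patients rated only at Week 1 would have no data in the model. That would need Week 1 to be the omitted visit and their termination rating to be missing or excluded, whereas the Appendix schedules a MADRS at the termination visit for patients who withdraw.

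**The two faults do not compound.** Omitting Week 1 reduces the random-intercept inflation (12.7% to 9.7%) and hardly changes Week 8 precision under an unstructured covariance (empirical SD 1.815 against 1.827).

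**The model is secondary.** The ANOVA on LOCF change scores is the main analysis, which limits the consequence if the MMRM is only supportive. But section K's closing sentence on the MMRM gives its Week 8 t-test a deciding role. That conflict is a separate matter to reconcile; while it stands, the specification of this model matters.

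**Conclusion.** The visit-count contradiction is certain: four levels in section K against five post-baseline MADRS ratings in section F and the Appendix, and against section K's own next sentence. It is an inconsistency to reconcile, not evidence that data will be dropped.

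The covariance point holds conditionally. If the model is fitted as written, with independent equal-variance residuals, the Week 8 test has its nominal level only when variance is about constant. With complete data at nominal 5%, the level is 2.5% for SD falling from 9 to 7, 6.6% for a rise from 7 to 8, and about 11% for a rise from 5 to 9 (about 5% at nominal 0.017), with more for a steeper rise. These figures rest on assumed SDs, and the simulations also on assumed correlations and dropout at random; the protocol supplies none of these except the 20% dropout rate. Confidence is high on the visit count. On the covariance it is high on the mechanism, but not on the size or direction in this trial.

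The model statement should be corrected. The matter is moderate rather than critical, given the secondary label.

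**What to change.** Amend two sentences in section K:

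- State that the visit factor has five levels: Weeks 1, 2, 4, 6 and 8.
- Replace the random subject effect with an unstructured within-subject covariance, fitted by REML with Kenward-Roger degrees of freedom. Name one fallback, such as heterogeneous Toeplitz or a sandwich variance, for use only if the unstructured fit does not converge. The degrees-of-freedom and fallback details may sit in the statistical analysis plan, provided that the protocol no longer states something different.

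The cost is 5 × 6/2 = 15 covariance parameters in place of 2, which 216 patients can support. Visit schedule, data collection and sample size are unchanged. Where variance does rise, the reported Week 8 standard error will be larger than under the random intercept (in the simulated 5-to-9 case 1.86 instead of 1.46). That is the removal of an understatement and not a real loss of precision.
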